6.3 Sample Size Determination

6.3.1 Power and Sample Size for Primary Objective

Assumptions for sample size calculations included:

- Two sample two sided t-test with equal variances
- 5% significance level, but superiority is only claimed if estimated difference in mean weight loss favors WMP + Rx (this corresponds to a one-sided test on a 2.5% significance level).
- 1:1 randomization
- 50% of subjects in both arms are expected to drop out (based on input from the Cleveland Clinic)
 - Among subjects who drop out, 50% are expected to return for a month 12 (visit 13) assessment (retrieved drop outs).
 - Retrieved and non-retrieved drop outs in the WMP arm are assumed to have the same effect as subjects who complete the WMP arm.
 - Non-retrieved drop outs in the WMP + Rx arm are assumed to have an effect corresponding to subjects in the WMP arm.
 - Retrieved drop outs in the WMP + Rx arm are assumed to have an effect corresponding to half the weight loss difference (compared to WMP) of subjects who complete the study in the WMP + Rx arm.
- The following expected distribution of prescriptions in the WMP + Rx arm (based on input from the Cleveland Clinic):
 - 0% Orlistat (Xenical®)
 - 10% Lorcaserin/Lorcaserin extended-release (Belviq®/BelviqXR)
 - 30% Phentermine/Topiramate extended-release (Qsymia®)
 - 30% Naltrexone/Bupropion extended-release (Contrave®)
 - 30% Liraglutide 3.0 mg (Saxenda®)

Table 6-1 presents several sample size scenarios and power calculations based on the above assumptions, varying expected mean differences in weight loss between treatment arms (treatment effect) over 1 year and standard deviations (SD) as the variation of weight loss between subjects within the same treatment arm. Treatment effect scenarios of 3, 3.5, 4, and 5% were chosen based on product labels. SD of 8, 9, 10, and 11 % were chosen based on the NN8022 (SCALE) program [18] [19] [20] and the TRAMOMTANA [21] study.

Table 6-1. Power calculations for selected total N, treatment effects, and standard deviations

	Treatment effect (%)															
	3				3.5				4				5			
	SD (%)				SD (%)				SD (%)				SD (%)			
Total N	8	9	10	11	8	9	10	11	8	9	10	11	8	9	10	11
160	0.65	0.55	0.47	0.40	0.79	0.69	0.59	0.52	0.88	0.80	0.71	0.63	0.98	0.94	0.88	0.82
180	0.71	0.60	0.52	0.44	0.83	0.74	0.65	0.56	0.92	0.84	0.76	0.68	0.99	0.96	0.92	0.86
200	0.75	0.65	0.56	0.48	0.87	0.78	0.69	0.61	0.94	0.88	0.80	0.73	0.99	0.97	0.94	0.89

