240	0.82	0.73	0.64	0.56	0.92	0.85	0.77	0.69	0.97	0.93	0.87	0.80	1.00	0.99	0.97	0.94
300	0.90	0.82	0.74	0.65	0.97	0.92	0.86	0.78	0.99	0.97	0.93	0.88	1.00	1.00	0.99	0.98

Total N = sum of subjects in both treatment arms; treatment effect = difference in one-year weight loss of WMP + Rx compared to WMP alone; standard deviation (SD) = variation in weight loss between subjects within the same treatment arm.

Based on the above mentioned assumptions and results from the referenced studies, a 4% treatment effect and 10% SD is a conservative, yet realistic scenario. Therefore, a total sample size of 200 subjects (100 subjects per treatment arm) with 80% power for the confirmatory hypothesis assuming a 25% attrition rate over 12 months was chosen.

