4.0 STATISTICAL METHODOLOGY

4.1 General Considerations

Statistical analyses will be performed using SAS® version 9.4 or higher computer software. Analyses will utilize prospectively collected data from study site at study visits as well as secondary data collection utilizing pharmacy dispensing data. Data from both sources will be integrated into one dataset for analysis.

Patient flow, patient characteristics, treatments, and outcomes will be tabulated and summarized with descriptive statistics based on observed values only. All descriptive data summaries will include means, medians, standard deviation (SD), and ranges for continuous variables and absolute/relative frequencies for categorical data. In addition, for each variable the number (count) of values that are missing will also be reported for dedicated study visit data. Missing data are data that are planned and can be collected but are absent. Statistics will be summarized for the study population overall and by treatment arm. Two sets of descriptive summaries will be produced: one based on the primary estimand (“intention-to-treat” (ITT)) and one based on the secondary estimand (“if all patients had adhered”).

Raw data (i.e., minimum and maximum values presented for range in continuous variables) will be reported out to the precision with which it was collected. Means will be reported to 1 decimal place more than the raw data. SD will be reported to 1 decimal place more than the mean. Percentages will be reported to 1 decimal place. Trailing zeros will be presented to maintain a consistent level of precision, e.g. 2.0 rather than 2.

Inferential tests will be performed at the 5% level of significance (two-sided). All p-values will be rounded to 3 decimal places. If a rounded p-value is 0.000 (i.e., the actual p-value is less than 0.0005), then the p-value will be presented as ‘p< 0.001.’

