5.6.3 Supplementary Analyses

The analysis of % weight change will be complemented with the following supplementary analyses. Analyses #3 and #4 will assess the potential impact of altering the mode of administering the SMAs, from on-site to virtual, during the trial in response to the COVID-19 outbreak.

Supplementary Analysis #1 (Completer analysis)

In the context of this first supplementary analysis, the analysis population will be defined as subjects in the FAS with month 12 (visit 13) body weight data who adhered to randomized treatment up to and including visit 13. Adherence is defined as for the secondary estimand for the primary endpoint in Section 5.6.2, i.e., subjects in the WMP arm will be considered non-adherent if/when criterion 1 above is met and subjects in the WMP + Rx arm will be considered non-adherent if/when either criterion 1 or 2 above is met. As an example, a subject in the WMP + Rx arm that misses visit 10, 11, and 12, but attends all other visits and is covered by prescription claims for at least 80% of the planned study duration, is considered a completer in this context if month 12 (visit 13) weight data are available. This analysis will use the same ANCOVA model described for the primary estimand analysis of the primary endpoint (Section 5.6.1).

Supplementary Analysis #2

For the second supplementary analysis, the analysis population will be defined as subjects in the FAS who remain in the CC EHP for the entirety of their study participation. Subjects who leave the Cleveland Clinic Employee Health Plan (CC EHP) and end study participation or leave the CC EHP but continue to attend SMAs and take study medication if in the WMP + Rx arm will be excluded from the analysis. Analysis of this subset of subjects will include missing body weight data imputation as described in the Section 5.5.1. Change in percent body weight will be analyzed and presented as described for the primary estimand analysis of the primary endpoint (Section 5.6.1).

Supplementary Analysis #3

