For the third supplementary analysis, a subgroup analysis will be performed based on the FAS and using the imputed weight data derived for the analysis of the primary estimand for the primary endpoint (Section 5.5.1). This analysis will use the same ANCOVA model described for the primary estimand analysis of the primary endpoint (Section 5.6.1), but with the addition of an interaction term composed of randomized treatment and mode of MN12 SMA administration (on-site or virtual) to the regression model. This interaction term will serve as a test for whether or not the observed treatment effect was consistent between those subjects who had an on-site MN12 SMA and those subjects who had a virtual MN12 SMA (H_0 : treatment effect [on-site MN12 SMA] = treatment effect [virtual MN12 SMA]). In the event of a significant interaction effect, the treatment difference between WMP + Rx and WMP alone will be presented as

described for the primary estimand analysis of the primary endpoint but stratified by mode of MN12 SMA administration.

Supplementary Analysis #4

In the context of this fourth supplementary analysis, the analysis of the secondary estimand of the primary endpoint will be repeated and results summarized per the method outlined in Section 5.6.2, but with the additional exclusion of body weight data collected after the transition to virtual SMAs. This analysis will use a MMRM and all body weight assessments from subjects who were adherent to the randomized treatment until end of treatment or until the transition to virtual SMAs (whichever occurred first), or up until the subject was considered non-adherent to the randomized treatment prior to the transition to virtual SMAs per the adherence criteria noted in Section 5.6.2.

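### Supplementary Analysis #3 plans treatment differences by SMA mode only after a significant interaction, a condition with low power in a trial sized for its main effect

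*SAP*

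**What the plan says.** SAP 5.6.3 gives the purpose of the two COVID-19 additions: "Analyses #3 and #4 will assess the potential impact of altering the mode of administering the SMAs, from on-site to virtual". Supplementary Analysis #3 uses the FAS and the month-12 weights imputed under SAP 5.5.1. It takes the primary ANCOVA and adds a term combining randomized treatment with the mode of the month-12 SMA. The null hypothesis is that the treatment effect is equal in the two modes, and the term is described as the test of whether the effect was consistent. The reporting rule then begins "In the event of a significant interaction effect, the treatment difference between WMP + Rx and WMP alone will be presented as" and continues with the primary-analysis format, stratified by mode. No by-mode presentation is planned after a non-significant result. SAP 4.1 sets the level at 5%, two-sided.

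The added term is the only one named; a main effect of mode is not mentioned. No power, virtual share or expected size of interaction is given.

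The trial was sized for something else. Protocol 6.3.1 describes "a total sample size of 200 subjects (100 subjects per treatment arm) with 80% power for the confirmatory hypothesis", on the basis that "a 4% treatment effect and 10% SD is a conservative, yet realistic scenario".

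**The concern.** An interaction is estimated with much less precision than a main effect. A trial with 80% power for its main effect will usually fail to reach significance on an interaction of the same size. If significance decides whether the by-mode differences appear at all, a reader will usually be left with a p-value and no indication of how large a difference the data could exclude. The SAP's own description invites that p-value to be read as evidence of consistency.

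Analysis #3 is the only primary-estimand analysis that compares the two modes. It was added after the first patient's first visit specifically to judge whether moving the SMAs online altered the findings, so the rule bears directly on the question it was written to answer.

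**Working it through.** **Inputs from the documents.** Two-sided 5% level (SAP 4.1); "Two sample two sided t-test with equal variances" and "1:1 randomization", a 4-point effect, SD 10, N=200 and 25% attrition (Protocol 6.3.1); WMP-arm imputation applied to both arms, without SMA mode in the model (SAP 5.5.1).

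**Assumptions, because the documents are silent.** Virtual share p of 20-50%; virtual SMAs remove all of the 4-point effect or half of it; 1:1 arms within each mode; mode known for every subject, although the SAP does not say how it is assigned to someone with no month-12 SMA.

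**1. The plan's own figure.** SE of the main effect = 10 × √(2/100) = 1.414, and 4/1.414 = 2.83. Power is 0.807 by the normal approximation and 0.804 by noncentral t, against 0.80 stated.

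**2. Interaction power, complete data, mode main effect included.** SE = 2 × SD / √(N p (1−p)), noncentral t with N−5 df, SD 10, N=200:

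| Virtual share | SE | Power, 4-point loss | Power, 2-point loss |
|---|---|---|---|
| 20% | 20/√32 = 3.54 | 20.3% | 8.7% |
| 30% | 20/√42 = 3.09 | 25.2% | 9.9% |
| 50% | 20/√50 = 2.83 | 29.1% | 10.8% |

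Even at an even split the SE is twice that of the main effect. Power of 80% for a 4-point interaction would then need about 788 subjects. Sensitivity for total loss:
- 10% virtual: 13.5%.
- N=150 in place of 200: 16-23% over 20-50% virtual.
- SD 8 to 11 at an even split: 42% down to 25%.

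**3. With the planned imputation.** Imputed subjects in both arms come from a WMP-only model, so they carry no treatment effect in either mode and shrink the interaction. The simulations used 25% missing, imputation from observed WMP subjects, Rubin pooling, a mode main effect and total loss under virtual SMAs. They used fewer imputations than the planned 100. Power at 20%, 30% and 50% virtual:
- 4 points among observed subjects (4 × 0.75 = 3 net): about 6%, 8% and 9%.
- 4 points net (5.33 × 0.75 = 4): about 9%, 13% and 17%.

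With no interaction, the rejection rate was about 1-2%, not 5%. Part of the drop from step 2 is therefore conservative Rubin pooling under reference-based imputation, and part is dilution.

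**4. The model read literally, without a mode main effect.** Simulated power for total loss rises to about 14-40%. But the term then compares virtual with on-site among WMP + Rx subjects. With equal treatment effects and a 3-point mode shift in both arms, it rejected in about 9% (30% virtual) and 10% (50% virtual) of runs, so it is not a clean test of the stated null hypothesis.

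**5. Precision if the estimates were always shown.** Half-width = 1.96 × 10 × √(2/n per arm in that mode). At 50/50 (50 per arm) it is 3.9 points in each mode. At 20% virtual it is 6.2 points for virtual (20 per arm) and 3.1 for on-site (80 per arm).

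**The case against.** Showing subgroup effects only after an interaction test is a familiar restraint against over-reading noisy strata, and SAP 4.9 plans no subgroup analyses. Analysis #3 is supplementary and leaves the single confirmatory test untouched. At 20% virtual, an interval of about ±6 points around a planned 4-point effect would rarely settle the matter. All of that stands, and it makes this a reporting improvement. It does not support the condition: a wide interval shows what the data cannot exclude, whereas a lone non-significant p-value hides it.

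A reader might infer that a loss of effect under virtual SMAs would almost always go unreported, with nothing else shown. The documents do not support that. The interaction test is itself a planned output, and the SAP does not forbid showing the strata after a non-significant result; it simply does not plan it. Supplementary Analysis #4 is reported unconditionally. However, it uses the secondary estimand and excludes weights taken after the transition, so it gives no estimate of the effect under virtual SMAs.

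Nor can one narrow power figure be attached to the rule. The result depends on the virtual share, the size of the loss, whether 4 points is net or observed, and a mode main effect that the SAP does not name. With complete data, total loss would be missed about 71-80% of the time, which is often but not almost always.

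**Conclusion.** The concern holds in this form: the by-mode estimates depend on a low-power test, so a real difference by mode would usually leave them unpresented.

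At N=200 and SD 10, with complete data, a mode main effect and 20-50% virtual, power is about 20-29% for total loss of the 4-point effect and 9-11% for half. With the planned imputation, 25% missing and total loss, it is roughly 6-17%, depending on whether 4 points is observed or net. The literal model gives about 14-40%, on a term that does not cleanly test the stated hypothesis. None of these figures makes non-significance good evidence of consistency. The virtual share and the loss sizes are assumptions. The direction is secure because it follows from sizing the trial on the main effect.

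**What to change.** In SAP 5.6.3, Supplementary Analysis #3:
- Delete the condition on significance.
- Add a main effect of month-12 SMA mode to the model.
- Whatever the p-value, report the interaction estimate with its 95% CI, and the WMP + Rx minus WMP difference with its 95% CI for on-site and for virtual subjects.
- State that a non-significant interaction is not evidence of consistency.

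The cost is a few words in the SAP and one extra table whose intervals will be wide. The by-mode estimates will still be diluted by the reference-based imputation, which this change does not address; a footnote to the table should say so.

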5.7 Secondary Endpoints

5.7.1 Statistical Analysis for the Primary Estimand

The following analyses are planned to further support the primary objective to compare weight loss of WMP + Rx versus WMP. They will also address the secondary objectives of this study to compare WMP + Rx versus WMP with respect to categorical weight loss, WMP adherence, and PROs, as well as adherence to obesity medication within the WMP + Rx cohort.

All secondary analyses described in this section will be the primary estimand based on the FAS. No sensitivity analyses are planned for the secondary endpoints.

5.7.1.1 Categorical Weight Loss

For the categorical weight loss endpoints, subjects will be dichotomized based on body weight loss at month 12 (visit 13) compared to baseline. Analysis will use the imputed weight data derived for the analysis of the primary estimand for the primary endpoint (Section 5.5.1). For the first categorical weight loss endpoint, subjects will be grouped as those with 5% or more body weight loss and those with less than 5% loss. The proportion of subjects achieving the endpoint will be analyzed using a logistic regression model with treatment as categorical effect and baseline weight (kg) as covariate. From the model, the estimated odds ratio (OR) (WMP + Rx / WMP) will be presented, along with the two-sided 95% CI and corresponding p-value. An OR above 1.0 will be interpreted as favoring WMP + Rx. In addition, the predicted probability of achieving at least 5% body weight loss for an average trial subject in each treatment arm will be estimated from the model.

For the second categorical weight loss endpoint, subjects will be dichotomized as those with 10% or more body weight loss and those with less than 10% loss. The analysis will utilize the same approach described for the first categorical weight loss endpoint.

5.7.1.2 Adherence to Weight Management Program (WMP)

The WMP adherence endpoints will be assessed through SMA attendance during the course of the study. For the first WMP adherence endpoint, SMA attendance will be calculated for each subject as the percentage planned SMAs attended between baseline (month 0) and month 12 (visit 13), i.e., number of SMAs attended/12 planned SMAs. Attendance will be descriptively summarized by treatment arm.

For the second WMP adherence endpoint, the proportion of subjects attending ≥ 9 SMAs will be descriptively summarized as percentage of number of subjects in each treatment arm.

No formal statistical testing will be conducted for either endpoint.

5.7.1.3 Adherence to Obesity Medication

Adherence to obesity medication will be assessed through PDC (as defined in Section 4.8.4) for the WMP + Rx treatment arm only. The PDC and the proportion of subjects with at least 80% PDC will be descriptively summarized for the WMP + Rx treatment arm. No formal statistical testing will be conducted.

5.7.1.4 Patient Reported Outcome (PRO) Analysis

PROs will be measured with the instruments described in Section 4.8.6. Analysis of these measures will address the secondary objective of this study to compare WMP + Rx versus WMP in the study's patient population as is relates to PROs, i.e., work productivity and work limitations, over one-year observation period. PRO analysis will descriptively summarize these measures at baseline and month 12, as well as compare treatment arms for change from baseline.

The primary estimand for the PRO analysis will be based on the FAS with missing data imputation as described in the Section 5.5.2. Analysis of change for each instrument scale will follow the method described for the primary estimand for the primary endpoint: ANCOVA model with randomized treatment as a factor and baseline value of the endpoint variable as covariate. Estimated difference (WMP + Rx minus WMP) in change from baseline (month 0) to month 12 (visit 13) for each scale will be presented with 95% CI and corresponding p-value. If examination of the data indicate that it is not justifiable to model data based on assumptions of normality, e.g., many responses of 0% or close to 0%, alternative statistical modeling will be used (e.g. logistic regression after definition of a responder limit).

Change in PRO instrument scales will include:

- Change in WLQ-8: At-Work Productivity Loss index from baseline to month 12
- Change in WLQ-8: Time Management index from baseline to month 12
- Change in WLQ-8: Physical Tasks index from baseline to month 12
- Change in WLQ-8: Mental/Interpersonal Tasks index from baseline to month 12
- Change in WLQ-8: Output Tasks index from baseline to month 12

- Change in WPAI:SHP: Work time missed due to excess weight from baseline to month 12
- Change in WPAI:SHP: Impairment while working due to excess weight from baseline to month 12
- Change in WPAI:SHP: Overall work impairment due to excess weight from baseline to month 12
- Change in WPAI:SHP: Activity impairment due to excess weight from baseline to month 12

5.7.2 Statistical Analysis for the Secondary Estimand

5.7.2.1 Categorical Weight Loss

The secondary estimand for the categorical weight endpoint of $\geq 5\%$ reduction in body weight from baseline (5% responder) will be assessed using the MMRM for efficacy as described for the secondary estimand for the primary endpoint in Section 5.6.2. Analysis will only use assessments from subjects who are adherent to the randomized treatment until end of treatment, or up until the subject is considered non-adherent to the randomized treatment. From the MMRM, individually predicted values for % weight change at month 12 will be used to classify each subject as 5% responder or not. This classification will then be analyzed using a logistic regression model with treatment as the only factor. From the model, the estimated OR (WMP + Rx / WMP) will be presented with the 95% CI and p-value. In addition, the predicted probability of achieving at least 5% body weight loss for an average trial subject in each treatment arm will be estimated from the model.

The secondary estimand for the categorical weight endpoint of $\geq 10\%$ reduction of body weight from baseline (10% responder) will follow the same approach outlined for the 5% responder. The estimated OR (WMP + Rx / WMP), 95% CI and p-value will be presented, along with the predicted probability of achieving at least 10% body weight loss for an average trial subject in each treatment arm.

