3.2 Secondary Endpoints

All secondary study endpoints are to be considered supportive in nature. There are no pre-specified confirmatory secondary endpoints.

Supportive secondary endpoints of this study include:

- Subjects who after 12 months achieve (yes/no):
 - $\geq 5\%$ reduction in body weight from baseline
 - $\geq 10\%$ reduction in body weight from baseline
- Adherence to Cleveland Clinic's Integrated Medical WMP from baseline (month 0) to month 12 (visit 13), as:
 - Number of shared medical appointments (SMA) attended
 - Subjects attending ≥ 9 SMAs (yes/no)
- Adherence to medication for chronic weight management from baseline (month 0) to month 12 (visit 13) in the treatment arm randomized to the WMP in combination with medication for chronic weight management, as:
 - Proportion of days covered (PDC) by prescription claims for medication for chronic weight management
 - Subjects covered by prescription claims for medication for chronic weight management for at least 80% of days (yes/no)
- Change in PROs from baseline (month 0) to month 12 (visit 13) in
 - Work limitation as measured by Work Limitations Questionnaire Self-administered Short-Form (WLQ-8)
 - At-Work Productivity Loss Index (point)
 - Time Management (point)
 - Physical Tasks (point)
 - Mental/Interpersonal Tasks (point)

- Output Tasks (point)
- Work productivity as measured by Work Productivity and Activity Impairment Questionnaire Specific Health Problem V2.0 (WPAI:SHP)
 - Work time missed due to excess weight (%)
 - Impairment while working due to excess weight (%)
 - Overall work impairment due to excess weight (%)
 - Activity impairment due to excess weight (%)

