5.6.2 Statistical Analysis for the Secondary Estimand

The secondary estimand of the primary endpoint will address the efficacy of medication for chronic weight management if all subjects adhere to their randomized treatment (WMP + Rx or WMP). For the secondary estimand, the primary endpoint will be analyzed using a mixed model for repeated measurements (MMRM) including all subjects, but for subjects considered non-adherent to randomized treatment, only data prior to non-adherence will be used. Month 12 (visit 13) assessments for retrieved drop outs will not be used in this analysis. The MMRM for efficacy will only use assessments from subjects who are adherent to the randomized treatment until end of treatment, or up until the subject is considered non-adherent to the randomized treatment. Subjects in the WMP arm will be considered non-adherent if/when criterion 1 below is met. Subjects in the WMP + Rx arm will be considered non-adherent if/when criterion 1 or 2 is met:

1. Missing 4 SMA visits. In this case, the last assessment made prior to the 4th missed SMA visit will be used as the last assessment. This is also the case if, e.g., 4 SMA visits in a row are missed.
2. Period with no coverage of prescription claims according to PDC exceeds 20% of planned medication duration, or number of days from visit 1 to visit 13. For subjects that drop out early, the expected visit 13 date (derived from the subjects' planned SMA group visit) will be used to calculate planned study duration. The last assessment made prior to exceeding 20% of planned study duration with no prescription claims will be used as last assessment (as defined in Section 4.8.5).

The MMRM for efficacy will be fitted using % weight change with randomized treatment as factor and baseline body weight (kg) as covariate, all nested within visit. An unstructured covariance matrix for measurements within the same subject will be employed, assuming that measurements for different subjects are independent. From the model, treatment effect will be estimated and reported along with the associated 95% CI and corresponding p-value testing the null-hypothesis of no difference between treatment arms.

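### Responders under the secondary estimand are classified once from an MMRM prediction and analysed as if observed, which understates the odds ratio's uncertainty and tends to exaggerate a true difference

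*SAP*

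**What the plan says.** SAP 5.7.2.1 takes the efficacy MMRM of SAP 5.6.2 and states that "individually predicted values for % weight change at month 12 will be used to classify each subject as 5% responder or not". It continues: "This classification will then be analyzed using a logistic regression model with treatment as the only factor". An OR with 95% CI and p-value is reported, plus a predicted response probability per arm. The SAP applies the same steps to the 10% cut. Protocol 6.6 prescribes the method for the 5% cut only.

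The MMRM uses data only up to non-adherence, and "Month 12 (visit 13) assessments for retrieved drop outs will not be used in this analysis". Non-adherence means a fourth missed shared medical appointment or, in WMP + Rx only, more than 20% of planned duration without prescription coverage.

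Under the primary estimand the same two cuts are handled differently. SAP 5.7.1.1 uses the imputed weights of SAP 5.5.1: 100 imputations, each analysed separately and pooled with Rubin's formula.

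On status, SAP 3.2 says: "All secondary study endpoints are to be considered supportive in nature".

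**The concern.** A subject without a usable month-12 weight gets one best guess, which is turned into a yes or no and then counted as an observed outcome. This does harm in two ways.

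- **Uncertainty.** The logistic standard error depends only on the 0/1 counts, so it is the same whether those outcomes were measured or predicted. All predictions in an arm also share the error in that arm's estimated month-12 mean, so many classifications can flip together.
- **Direction.** A conditional mean lacks residual spread. The same mean difference is then larger relative to the spread of the values being cut, which usually pushes the arms' response rates apart.

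Many classifications could be predictions. Protocol 6.3.1 assumes 50% drop-out in both arms, and retrieved drop-outs' month-12 weights are not used here. Non-adherence is defined differently from drop-out, so the real share is unknown.

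At stake are the OR, CI, p-value and response probabilities for both cuts under the efficacy estimand. They would look firmer than they are and, if the arms differ, usually too favourable.

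The term for an individual prediction is also undefined. It could be conditional on the subject's own weights, or use fixed effects only.

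**Working it through.** **Inputs from the documents.** 100 subjects per arm, 12 monthly visits, two-sided 5% tests, and the sizing statement that "a 4% treatment effect and 10% SD is a conservative, yet realistic scenario".

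**The plan's own figure.** The only stated operating characteristic is 80% power for the primary endpoint. 4 / (10 × √(2/100)) = 2.83, and Φ(2.83 − 1.96) = 0.807 (noncentral t: 0.804), so it reproduces. Nothing comparable is given for the responder analysis.

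**Assumptions not in the documents.** Arm means, within-subject correlation, and the share and timing of non-adherence. Observed month-12 weights of adherent subjects are kept, which is the favourable reading.

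**Step 1: true OR at assumed means −7 and −3, SD 10.**
- 5% cut: Φ(0.2) = 0.579 and Φ(−0.2) = 0.421, so OR = (0.579/0.421)² = 1.90.
- 10% cut: Φ(−0.3) = 0.382 and Φ(−0.7) = 0.242, so OR = 1.94.

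**Step 2: direction.** If the last usable value correlates r with month 12, predictions have SD 10r. With half the values predicted, the response rate in an arm with mean m at cut c is 0.5Φ((c − m)/10) + 0.5Φ((c − m)/(10r)). At the 5% cut:

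| r | Rates | OR (true 1.90) |
|---|---|---|
| 0.9 | 0.584 / 0.416 | 1.96 |
| 0.7 | 0.596 / 0.404 | 2.17 |
| 0.5 | 0.617 / 0.383 | 2.60 |

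This is the large-sample shift alone, before estimation error.

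**Step 3: uncertainty.** With response rates near 58% and 42%, the logistic SE is √[2(1/58 + 1/42)] = 0.29, however many of the 200 outcomes are predictions.

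**Step 4: first simulation.** Unstructured MMRM, prediction conditional on the subject's own data, four covariance structures, three timings of the last usable visit, 25% or 50% non-adherence in each arm; 600 trials per scenario, with and without an effect (null means −5/−5). With no censoring, coverage was 95% and null rejection about 6%.

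| Scenario | OR | CI coverage | Null rejection |
|---|---|---|---|
| 5% cut, 50% non-adherent, spread over year | 2.21–2.64 | 69–85% | 12–24% |
| 5% cut, 50%, all timings | 1.96 (late) – 3.33 (early) | 50–93% | 7–36% |
| 5% cut, 25%, spread | 2.06–2.25 | 86–90% | 8–16% |
| 10% cut, 50%, spread | 2.14–2.31 | 85–91% | 8–12% |
| 10% cut, 25%, spread | 2.05–2.13 | 92–94% | not quoted |

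At 50% spread and the 5% cut, the plan's SE was 0.29 against an actual SD of the log-OR of 0.41 (random walk), and 0.30 against 0.47 (random walk plus noise).

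**Step 5: second simulation, built separately.** Means −9/−5, 5% cut, month-to-month correlation 0.95, 50% non-adherent, 1,200 trials per scenario. For early, spread and late loss the OR was about 2.8, 2.3 and 2.0 against 1.90, and coverage was 61%, 79% and 90%. Null rejection (both arms −5) was 39%, 22% and 10%, against 5–7% with complete data. The SE was too small in every scenario run.

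**Step 6: the plan against complete data.** In the second simulation (means −7/−3, 5% cut, 50% spread, correlation 0.95), the planned method gave p < 0.05 in 79% of trials, fully observed data in 61% and multiple imputation in 43%. Losing half the outcomes cannot add information, so the excess is spurious.

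**The case against.** - **Limited consequence.** These are supportive endpoints under the secondary estimand. The same cuts get a multiply imputed OR under the primary estimand, and the efficacy MMRM gives a direct estimate with CI for continuous weight change. This stands and limits the seriousness, but a nominal 95% interval should still cover close to 95%.
- **Placement and correlation.** Means of −7/−3 put the 5% cut midway between the arms, where predictions separate most, and the documents give no expected mean loss. This stands for size. With weak correlation and both means to one side of the cut, the exaggeration can vanish or reverse: r = 0.2, means −5/−1 and the 10% cut give 1.84 against a true 1.98, and the second simulation found 1.97–2.04 against 1.96–2.03 in such cases. Hence tends to, not always.
- **Extremes.** An OR of 3.33 needs half of each arm to have its last usable visit in months 1–5. The documents give no timing. Early loss is possible, since a subject who never fills a prescription reaches 20% of 365 days at day 73. That rule applies to one arm only, so the equal shares of the first simulation are a simplification.
- **The remedy is conservative.** With Rubin pooling, null rejection was 0.3–3.7%, so part of the loss of significant results comes from the remedy. This stands as a cost.
- **Fixed-effects-only reading.** Here only 20–32% of simulated trials gave a 5% OR without an empty cell. That partly reflects simulating no baseline-weight effect, so it supports defining the term and little more.

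**Conclusion.** The concern holds. The analysis as written treats predictions as observations, and no text corrects for it. The understated uncertainty does not depend on a particular covariance. Exaggeration of a true difference appeared in nearly all scenarios, but its size depends on the share and timing of non-adherence, the within-subject correlation and how near the arm means lie to the cut. With equal arms and equal non-adherence the OR is not shifted on average, but the test rejects too often. Late non-adherence with strongly correlated weights does little harm.

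The sizes are illustrations resting on the assumptions listed; the mechanism is certain. The change should be made, although the trial's confirmatory conclusion does not depend on it.

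**What to change.** In SAP 5.7.2.1, replace the single classification. Impute month-12 % weight change from the on-adherence data under the same MMRM (missing at random), with 100 imputations as in SAP 5.5.1. Classify 5% and 10% responders in each completed data set, fit the planned treatment-only logistic model and pool with Rubin's rules. Align Protocol 6.6 for the 5% cut, or document the departure. If predicted-value proportions are still shown, define the prediction and present them descriptively.

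In the first simulation this gave ORs of 1.85–1.89 (5% cut) and 1.90–1.96 (10% cut), with 96–99% coverage. Bootstrapping the whole procedure is an alternative if Rubin intervals are thought too wide; its performance was not simulated.

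The cost is modest programming, since PROC MI and PROC MIANALYZE are already planned. Standard errors rise by about 8% at 25% non-adherence and 19–22% at 50%. At 50%, trials with p < 0.05 at the assumed effect fall from 77–83% to 38–41%. The higher figure comes from a test that does not hold its 5% level, so it is not genuine power.
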